6.3.2 Supportive Care Guidelines

Subjects should receive appropriate supportive care measures as deemed necessary by the treating investigator. Suggested supportive care measures for the management of adverse events with potential immunologic etiology are outlined below. Where appropriate, these guidelines include the use of oral or intravenous treatment with corticosteroids as well as additional anti-inflammatory agents if symptoms do not improve with administration of corticosteroids. Note that several courses of steroid tapering may be necessary as symptoms may worsen when the steroid dose is decreased. For each disorder, attempts should be made to rule out other causes such as metastatic disease or bacterial or viral infection, which might require additional supportive care. The treatment guidelines are intended to be applied when the investigator determines the events to be related to pembrolizumab.

Note: if after the evaluation the event is determined not to be related, the investigator does not need to follow the treatment guidance (as outlined below). Refer to Section 5.2.1 for dose modification.

It may be necessary to perform conditional procedures such as bronchoscopy, endoscopy, or skin photography as part of evaluation of the event.

- Pneumonitis:
 - For Grade 2 events, treat with systemic corticosteroids. When symptoms improve to Grade 1 or less, steroid taper should be started and continued over no less than 4 weeks.
 - For Grade 3-4 events, immediately treat with intravenous steroids.
 Administer additional anti-inflammatory measures, as needed.
 - Add prophylactic antibiotics for opportunistic infections in the case of prolonged steroid administration.
- Diarrhea/Colitis:

Subjects should be carefully monitored for signs and symptoms of enterocolitis (such as diarrhea, abdominal pain, blood or mucus in stool, with or without fever) and of bowel perforation (such as peritoneal signs and ileus).

- All subjects who experience diarrhea/colitis should be advised to drink liberal quantities of clear fluids. If sufficient oral fluid intake is not feasible, fluid and electrolytes should be substituted via IV infusion. For Grade 2 or higher diarrhea, consider GI consultation and endoscopy to confirm or rule out colitis.
- For Grade 2 diarrhea/colitis, administer oral corticosteroids.
- For Grade 3 or 4 diarrhea/colitis, treat with intravenous steroids followed by high dose oral steroids.
- When symptoms improve to Grade 1 or less, steroid taper should be started and continued over no less than 4 weeks.
- Type 1 diabetes mellitus (if new onset, including diabetic ketoacidosis [DKA]) or ≥ Grade 3 Hyperglycemia, if associated with ketosis (ketonuria) or metabolic acidosis (DKA)
 - For **T1DM** or **Grade 3-4** Hyperglycemia
 - Insulin replacement therapy is recommended for Type I diabetes mellitus and for Grade 3-4 hyperglycemia associated with metabolic acidosis or ketonuria.
 - Evaluate patients with serum glucose and a metabolic panel, urine ketones, glycosylated hemoglobin, and C-peptide.
- Hypophysitis:
 - For Grade 2 events, treat with corticosteroids. When symptoms improve to Grade 1 or less, steroid taper should be started and continued over no less than 4 weeks. Replacement of appropriate hormones may be required as the steroid dose is tapered.
 - For Grade 3-4 events, treat with an initial dose of IV corticosteroids followed by oral corticosteroids. When symptoms improve to Grade 1 or less, steroid taper should be started and continued over no less than 4 weeks. Replacement of appropriate hormones may be required as the steroid dose is tapered.

• Hyperthyroidism or Hypothyroidism:

Thyroid disorders can occur at any time during treatment. Monitor patients for changes in thyroid function (at the start of treatment, periodically during treatment, and as indicated based on clinical evaluation) and for clinical signs and symptoms of thyroid disorders.

- Grade 2 hyperthyroidism events (and Grade 2-4 hypothyroidism):
 - In hyperthyroidism, non-selective beta-blockers (e.g. propranolol) are suggested as initial therapy.
 - In hypothyroidism, thyroid hormone replacement therapy, with levothyroxine or liothyronine, is indicated per standard of care.
- **Grade 3-4** hyperthyroidism
 - Treat with an initial dose of IV corticosteroid followed by oral corticosteroids. When symptoms improve to Grade 1 or less, steroid taper should be started and continued over no less than 4 weeks. Replacement of appropriate hormones may be required as the steroid dose is tapered.
- Hepatic:
 - For Grade 2 events, monitor liver function tests more frequently until returned to baseline values (consider weekly).
 - Treat with IV or oral corticosteroids
 - For Grade 3-4 events, treat with intravenous corticosteroids for 24 to 48 hours.
 - When symptoms improve to Grade 1 or less, a steroid taper should be started and continued over no less than 4 weeks.

• Renal Failure or Nephritis:

- For **Grade 2** events, treat with corticosteroids.
- For **Grade 3-4** events, treat with systemic corticosteroids.
- When symptoms improve to Grade 1 or less, steroid taper should be started and continued over no less than 4 weeks.

• **Management of Infusion Reactions**: Signs and symptoms usually develop during or shortly after drug infusion and generally resolve completely within 24 hours of completion of infusion.

Table 4 below shows treatment guidelines for subjects who experience an infusion reaction associated with administration of pembrolizumab (MK-3475).

NCI CTCAE Grade	Treatment	Premedication at subsequen dosing
Grade 1 Mild reaction; infusion interruption not indicated; intervention not	Increase monitoring of vital signs as medically indicated until the subject is deemed medically stable in the opinion of the	None
ndicated	investigator.	
Grade 2 Requires infusion interruption but responds promptly to symptomatic treatment (e.g., antihistamines, NSAIDS, narcotics, IV fluids); prophylactic medications indicated for < =24 hrs	Stop Infusion and monitor symptoms. Additional appropriate medical therapy may include but is not limited to: IV fluids Antihistamines NSAIDS Acetaminophen Narcotics Increase monitoring of vital signs as medically indicated until the subject is deemed medically stable in the opinion of the investigator. If symptoms resolve within one hour of stopping drug infusion, the infusion may be restarted at 50% of the original infusion rate (e.g., from 100 mL/hr to 50 mL/hr). Otherwise dosing will be held until symptoms resolve and the subject should be premedicated for the next scheduled dose. Subjects who develop Grade 2 toxicity despite adequate premedication should be permanently discontinued from further trial treatment administration.	Subject may be premedicated 1.5h (± 30 minutes) prior to infusion of pembrolizumab (Mk 3475) with: Diphenhydramine 50 mg po (or equivalent dose of antihistamine). Acetaminophen 500-1000 mg po (or equivalent dose of antipyretic).
Grades 3 or 4 Grade 3: Prolonged (i.e., not rapidly responsive to symptomatic medication and/or brief interruption of infusion); recurrence of symptoms following initial mprovement; hospitalization ndicated for other clinical sequelae (e.g., renal impairment, pulmonary nfiltrates) Grade 4: Life-threatening; pressor or ventilatory support indicated	Stop Infusion. Additional appropriate medical therapy may include but is not limited to: IV fluids Antihistamines NSAIDS Acetaminophen Narcotics Oxygen Pressors Corticosteroids Epinephrine Increase monitoring of vital signs as medically indicated until the subject is deemed medically stable in the opinion of the investigator. Hospitalization may be indicated. Subject is permanently discontinued from further trial treatment administration.	No subsequent dosing

Table 2 - Infusion Reaction Treatment Guidelines

6.4 Concomitant Medication and Treatment

AIO-Studien-gGmbH

Patients may continue their baseline medication(s) according to the recommendations of the responsible physician. All concomitant medication(s) must be reported in the eCRF. Any therapeutic, or surgical procedure performed during the study period should be recorded including the dates, description of the procedure(s) and any clinical findings. Patients should receive full supportive care including transfusion of blood and products, antibiotics, etc. where applicable. The treatment details have to be recorded in the eCRF.

All concomitant medications received within 28 days before the first dose of trial treatment and 21 days after the last dose of trial treatment should be recorded. Concomitant medications administered after 21 days after the last dose of trial treatment should be recorded for SAEs and events of clinical interest (ECIs).

Additionally, any diagnostic, therapeutic or surgical procedure performed during the study period should be recorded.

Supportive care for treatment-related symptoms will be offered as needed to all patients in this study.

Prohibited Medications

Medications or vaccinations specifically prohibited in the exclusion criteria are not allowed during the ongoing trial. If there is a clinical indication for one of these or other medications or vaccinations specifically prohibited during the trial, discontinuation from trial therapy or vaccination may be required. The investigator should discuss any questions regarding this with the Sponsor. The final decision on any supportive therapy or vaccination rests with the investigator and/or the subject's primary physician.

Subjects are prohibited from receiving the following therapies during the Screening and Treatment Phase (including retreatment for post-complete response relapse) of this trial:

- Antineoplastic systemic chemotherapy or biological therapy
- Immunotherapy not specified in this protocol
- Chemotherapy not specified in this protocol
- Investigational agents other than pembrolizumab
- Radiation therapy

AIO-Studien-gGmbH

- Live vaccines within 30 days prior to the first dose of trial treatment and while participating in the trial. Examples of live vaccines include, but are not limited to, the following: measles, mumps, rubella, varicella/zoster, yellow fever, rabies, BCG, and typhoid vaccine.
- Systemic glucocorticoids for any purpose other than to modulate symptoms from an event of clinical interest of suspected immunologic etiology. The use of physiologic doses of corticosteroids may be approved after consultation with the Sponsor.

Subjects who, in the assessment by the investigator, require the use of any of the aforementioned treatments for clinical management should be removed from the trial. Subjects may receive other medications that the investigator deems to be medically necessary.

There are no prohibited therapies during the Post-Treatment Follow-up Phase.

7 Assessment of Safety

It is the responsibility of the investigators to report all adverse events in the case report form. Any serious adverse event (SAE) must be reported within 24 hours to the safety desk who will forward the SAEs to the Coordinating Investigator, sponsor and MSD within one working day.

Contact details for safety reporting are provided in the Investigator Site File.

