7.2.3 AEs of Special Interest (Events of Clinical Interest)

Events of clinical interest for this trial are:

- 1. an overdose of pembrolizumab, as defined in Section 7.2.6, that is not associated with clinical symptoms or abnormal laboratory results.
- 2. an elevated AST or ALT lab value that is greater than or equal to 3X the upper limit of normal and an elevated total bilirubin lab value that is greater than or equal to 2X the upper limit of normal and, at the same time, an alkaline

phosphatase lab value that is less than 2X the upper limit of normal, as determined by way of protocol-specified laboratory testing or unscheduled laboratory testing.*

*Note: These criteria are based upon available regulatory guidance documents. The purpose of the criteria is to specify a threshold of abnormal hepatic tests that may require an additional evaluation for an underlying etiology.

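### Read literally, the steroid rule in protocol 6.4 prohibits most of the steroid treatment that 6.3.2 and Table 2 call for, because it is tied to the two-item list in 7.2.3

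*Protocol*

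**What the plan says.** Protocol 6.4 opens its list with "Subjects are prohibited from receiving the following therapies during the Screening and Treatment Phase". The last item is "Systemic glucocorticoids for any purpose other than to modulate symptoms from an event of clinical interest of suspected immunologic etiology". One further allowance follows: "The use of physiologic doses of corticosteroids may be approved after consultation with the Sponsor". Subjects who, in the investigator's assessment, "require the use of any of the aforementioned treatments for clinical management should be removed from the trial". The section closes with "There are no prohibited therapies during the Post-Treatment Follow-up Phase".

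The key term is defined in 7.2.3, which begins "Events of clinical interest for this trial are" and gives two items. The first is an overdose "that is not associated with clinical symptoms or abnormal laboratory results". The second is AST or ALT at least 3 times the upper limit of normal, with total bilirubin at least 2 times and alkaline phosphatase below 2 times that limit.

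Section 6.3.2 sets out corticosteroid treatment for a range of immune-mediated events, and Table 2 lists corticosteroids among the options for Grade 3-4 infusion reactions. Table 1 in 6.3.1 holds treatment for several of these events, allows restart once toxicity falls to Grade 0-1, and sets limits on how long the steroid may be continued.

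SAP 2.9 names prohibited therapy during screening and treatment, as the protocol defines it, among the deviations that may be judged relevant. Relevant deviations lead to exclusion from PP. SAP 5 makes PP the primary efficacy set and repeats the analyses on ITT.

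**The concern.** The 6.4 exception borrows a term whose definition serves expedited reporting and does not describe the immune events for which this drug's toxicity is treated with steroids. An investigator who follows 6.3.2 for, say, Grade 2 pneumonitis is on the wording of 6.4 giving a prohibited drug, and should remove from the trial a patient whom Table 1 may allow to continue. The same wording reaches the analysis, because SAP 2.9 takes its list of prohibited therapies from the protocol. Withdrawn patients are not replaced (5.3), and the trial has 30.

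**Working it through.** No figure in the plan needs reproducing for the main point; it is a comparison of texts, followed by timing and size.

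**1. Steroid instructions against the 7.2.3 list**

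| Event | Steroids called for (6.3.2, Table 2) | On the 7.2.3 list? | Restart possible (Table 1) |
|---|---|---|---|
| Pneumonitis | Grade 2 and above | No | Grade 2 |
| Diarrhea/colitis | Grade 2 and above | No | Grade 2-3 |
| Hypophysitis | Grade 2 and above | No | Grade 2-4 |
| Renal failure/nephritis | Grade 2 and above | No | Grade 2 |
| Hepatic | Grade 2 and above | Only if the full pattern is met | Grade 2 |
| Hyperthyroidism | Grade 3-4 | No | Grade 3 |
| Infusion reaction | Grade 3-4, as an option | No | None at these grades |

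Only hepatic events can fall within the exception. Alkaline phosphatase is not in the chemistry panels of 5.2.1 to 5.2.5 or footnote 5 of the schedule, so confirming the pattern takes an unscheduled test. The other listed item, a symptom-free overdose, leaves no symptoms for a steroid to modulate.

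**2. Where the restart conflict can arise**

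Two doses are given: V1 on Day 1 and V2 on Day 21 +/- 3, that is Day 18 to 24. After V2 there is no dose to resume. The contradiction between removal (6.4) and restart (Table 1) therefore needs onset after V1 and before V2, about three weeks.

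Two rules narrow it further. For most of these events 6.3.2 asks for a taper of at least 4 weeks once symptoms reach Grade 1 or less, and 5.3 removes patients from further treatment if it is delayed by more than 6 weeks. Assuming the delay is counted from a nominal V2 on Day 21, the last restart day is 21 + 42 = Day 63. If the site also waits for the taper to finish, which Table 1 does not require, improvement must come by 63 - 28 = Day 35.

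**3. Where only removal and PP status are at issue**

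For onset after V2, and for grades that Table 1 discontinues permanently, there is no restart to contradict. The length of this period depends on where the Treatment Phase ends:

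- On the schedule's labels (V1 and V2 only), it ends by the pre-surgery visit, Day 43-50: 43/7 = 6.1 to 50/7 = 7.1 weeks.
- If it runs to the End of Treatment visit, about 4 weeks after discharge at Day 60-74 (3.2), it ends at about 60 + 28 = Day 88 to 74 + 28 = Day 102: 12.6 to 14.6 weeks.

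Nothing is prohibited in follow-up. Under 3.1, patients with non-tolerable toxicity during immunotherapy enter it after an End of Treatment visit.

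**4. Size of one PP exclusion**

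Table 3 plans on a pathologic response of 43% with an interval of 25.2 to 62.3, which is 62.3 - 25.2 = 37.1 points wide. Taking 13/30 = 43.3% as the illustration:

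- one responder excluded: 12/29 = 41.4%, a change of -2.0 points;
- one non-responder excluded: 13/29 = 44.8%, a change of +1.5 points.

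**The case against.** The strongest reply is that nobody would read 6.4 this way. The literal reading nearly empties the exception. The phrase about suspected immunologic etiology parallels the stated scope of 6.3.2. Section 6.3.1 points to 6.3.2 for corticosteroid use, Table 1's steroid limits presuppose steroid use, and 7.6.4 refers the treatment of events of clinical interest to 6.3.2. Section 6.4 promises supportive care for treatment-related symptoms to all patients and adds "The final decision on any supportive therapy or vaccination rests with the investigator" and/or the primary physician. It also says, more mildly, that discontinuation of trial therapy may be required when a prohibited drug is indicated. Section 6.3.2 introduces its measures as suggestions, although the individual bullets are written as instructions.

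Most of this stands, and it settles the intent. A reader might infer that patients would be denied steroids for immune toxicity; the documents do not support that. But the investigator's final say concerns whether to give the therapy. It does not cancel the removal sentence, nor make the drug a permitted one for SAP 2.9.

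The reply is also right that PP exclusion is not automatic. SAP 2.9 calls a deviation relevant only if it may influence the efficacy analysis, and leaves the classification to the data review meeting.

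**Conclusion.** The mismatch is real and stands in the current text, but it is minor: a slip in terminology and not a deliberate ban. It covers every steroid instruction in 6.3.2 and Table 2 except hepatic events that meet the 7.2.3 pattern. Its consequences are a removal instruction at odds with Table 1 for events starting between V1 and V2, and an optional route to PP exclusion at any point in the Treatment Phase.

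The effect on results is small. One exclusion moves the illustrative response rate by -2.0 or +1.5 points, efficacy is repeated on ITT, SAP 5.3 plans no tests, and adverse events are analysed on the Safety population.

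A reader might add the drug-related serious pneumonitis (1.6%) and colitis (0.9%) rates in 1.2.4 and infer a likely loss from PP: 30 x 0.025 = 0.75 patients, and 1 - 0.975^30 = 53% for at least one event. The documents do not support that inference. Those rates are not limited to onset in the affected window or to grades that allow restart. Pneumonitis is 1.6 of the 2.5 points, and Table 1 discontinues it permanently at Grade 3-4. The rates also omit non-serious Grade 2 events. Nothing says how often the meeting would call steroid use relevant, so no exclusion probability can be given.

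Nor should one infer that such patients would fail the endpoint of treatment in compliance with protocol. The documents do not say how it treats concomitant drugs, and Table 3 ties it to feasibility of resection.

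**What to change.** Reword the exception in 6.4 so that the prohibited item reads: *systemic glucocorticoids, except when given for adverse events of suspected immunologic etiology managed under 6.3.2, or for infusion reactions under Table 2*. Keep the sentence on physiologic doses. Leave 7.2.3 unchanged; widening it would extend 24-hour reporting to events it was not written for.

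SAP 2.9 then follows by reference, because it relies on the protocol's definition. A clarifying note there is optional, and the data review meeting keeps its judgement.

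The cost is one clause in a protocol amendment, with no new data or analysis. The small downside is that PP may keep an occasional steroid-treated patient.

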7.1 Reference safety documents

The current version of the Investigator's Brochure of Pembrolizumab will be used as reference document and will be provided to the investigators in the Investigator's File.

7.2 Adverse Events definitions

7.2.1 Adverse Events

An adverse event (AE) is defined in the International Conference on Harmonization (ICH) Guideline for Good Clinical Practice as "any untoward medical occurrence in a patient or clinical investigation subject administered a pharmaceutical product and which does not necessarily have a causal relationship with this treatment." (ICH E6: section 1.2).

An adverse event can therefore be any unfavorable and unintended sign (including an abnormal laboratory finding, for example), symptom, or disease temporally associated with the use of a medicinal (investigational) product, whether or not considered related to the medicinal (investigational) product.

7.2.2 Serious Adverse Event

A serious adverse event (SAE) is defined as any untoward medical occurrence (adverse event) that at any dose:

• results in death,

- is life-threatening (subject was at immediate risk of death at the time of the event),
- requires in-patient hospitalization or prolongation of existing hospitalization,
- results in persistent or significant disability/incapacity,
- is a congenital anomaly / birth defect or,
- any other significant medical condition.

A hospitalization meeting the regulatory definition for "serious" is any inpatient hospital admission that includes a minimum of an overnight stay in a health care facility. Any adverse event that does not meet one of the definitions of serious i.e. important medical events that may not be immediately life-threatening or result in death or hospitalization but may jeopardize the patient or may require interventions to prevent one of the other outcomes listed above (e.g. emergency room visit, outpatient surgery, or requires urgent investigation) may be considered by the investigator to meet the "other significant medical condition" criterion for classification as a serious adverse event. Examples include allergic bronchospasm, convulsions, and blood dyscrasias.

Hospitalization for performing of protocol-required procedures or administration of study treatment or hospitalizations for procedures planned prior to study start and elective hospitalizations are not classified as an SAE.

Progression of the underlying malignant disease and symptoms caused by progression of the underlying tumor disease need not to be reported as SAE in this protocol, unless progression or symptoms of progression are assessed as causally related to study medication.

7.2.3 AEs of Special Interest (Events of Clinical Interest)

Events of clinical interest for this trial are:

- 1. an overdose of pembrolizumab, as defined in Section 7.2.6, that is not associated with clinical symptoms or abnormal laboratory results.
- 2. an elevated AST or ALT lab value that is greater than or equal to 3X the upper limit of normal and an elevated total bilirubin lab value that is greater than or equal to 2X the upper limit of normal and, at the same time, an alkaline

phosphatase lab value that is less than 2X the upper limit of normal, as determined by way of protocol-specified laboratory testing or unscheduled laboratory testing.*

*Note: These criteria are based upon available regulatory guidance documents. The purpose of the criteria is to specify a threshold of abnormal hepatic tests that may require an additional evaluation for an underlying etiology.

